**Table 2. Operating Characteristics with Batch Size of 6 Subjects**

True DLT rate	R/R AML		MRD+ AML	
	Probability of early stopping of dose expansion	Average dose expansion sample size*	Probability of early stopping of dose expansion	Average dose expansion sample size*
0.10	3.8%	38.9	3.9%	48.5
0.20	34.0%	31.5	37.8%	37.8
0.25	58.2%	25.6	64.9%	29.4
0.30	78.9%	19.9	85.5%	21.6
0.35	91.6%	15.4	95.7%	16.0
0.40	97.4%	12.2	99.1%	12.3
0.50	99.9%	8.7	100%	8.7

AML = acute myeloid leukemia, MRD+ = minimal/measurable residual disease-positive, R/R = relapsed/refractory.

\* The average dose expansion sample size assumes early termination of the study whenever the rules to pause study enrollment are met.

### Efficacy Futility Rules during Dose Expansion

During dose expansion, Amgen will conduct evaluations of the ongoing overall response rate to assess if the threshold for early trial termination for futility has been reached. **For R/R AML**, a response consists of any of the following efficacious outcomes: CR, CR with incomplete recovery of peripheral blood counts (CRi), morphologic leukemia-free state,

partial remission and complete response/**remission** with partial hematologic recovery (CRh). An overall response rate less than 15% is considered insufficient efficacy. Amgen proposes stopping enrollment to the dose expansion cohorts early if any of the following occurs.

- None of the initial 12 subjects treated experience a response
- 2 or fewer of the initial 18 subjects treated experience a response
- 3 or fewer of the initial 24 subjects treated experience a response

Using these futility stopping rules, [Table 3](#) shows the probability of early stopping and the average sample size in dose expansion

**Table 3. Probability of Early Stopping and the Average Sample Size in R/R AML Dose Expansion**

True overall response rate	Probability of early stopping after 12 or fewer subjects	Probability of early stopping after 18 or fewer subjects	Probability of early stopping after 24 or fewer subjects	Average sample size
0.05	0.54	0.94	0.98	15.5
0.10	0.28	0.74	0.82	20.7
0.15	0.14	0.49	0.58	27.0
0.20	0.07	0.28	0.34	32.5
0.30	0.01	0.06	0.07	38.3

[REDACTED]

[REDACTED]. A conversion rate from MRD+ to MRD- < 25% is considered insufficient efficacy. Amgen proposes stopping enrollment to the dose expansion cohorts early if any of the following occurs:

- 2 or fewer of the initial 12 subjects treated experience a response
- 4 or fewer of the initial 18 subjects treated experience a response
- 5 or fewer of the initial 24 subjects treated experience a response

Using these futility stopping rules, [Table 4](#) shows the probability of early stopping and the average sample size in dose expansion.

**Table 4. Probability of Early Stopping and the Average Sample Size in MRD+ AML Dose Expansion**

True overall response rate	Probability of early stopping after 12 or fewer subjects	Probability of early stopping after 18 or fewer subjects	Probability of early stopping after 24 or fewer subjects	Average sample size
0.05	0.98	1.00	1	12.1
0.15	0.74	0.90	0.92	16.2
0.25	0.39	0.56	0.60	28.7
0.35	0.15	0.23	0.24	41.4
0.45	0.04	0.06	0.06	47.7

**Siltuximab Safety Stopping Rules:**

Amgen will conduct evaluations of the treatment and outcome of the CRS events treated with siltuximab on an ongoing basis to assess if the threshold for pausing siltuximab treatment has been reached as outlined in the table below. If these stopping rules are met, an adhoc DLRM will be triggered to review safety data and available pharmacokinetic, pharmacodynamics, and efficacy data. If recommended by DLRT, the use of siltuximab will resume. The stopping rules to trigger an adhoc DLRM to review siltuximab treatment use a Bayesian approach proposed by [Thall, et al \(1995\)](#); an adhoc DLRM will be triggered if the posterior probability that the CRS progression to Grade 3 rate is greater than 20% is  $> 80\%$  or the posterior probability that the CRS progression to Grade 4 rate is greater than 7.5% is  $> 80\%$ ; or observation of any grade 5 CRS after the event has been treated with siltuximab. The stopping boundaries presented below assume a prior distribution of Beta (0.4, 1.6) for progression to grade 3 CRS and a prior distribution of Beta (0.15, 1.85) for progression to grade 4 CRS. The evaluations could occur more frequently if necessary to address emerging safety concerns. If the triggered adhoc DLRM coincide with regular DLRM, they may be combined.

Number of Subjects Treated with Siltuximab	Trigger DLRM if severity of any CRS event treated with siltuximab progresses to Grade 5	
	Or this number of subjects with severity of CRS progressed to Grade 3 after being treated with siltuximab	Or this number of subjects with severity of CRS progressed to Grade 4 after being treated with siltuximab
5	$\geq 3$	$\geq 2$

10	≥ 4	≥ 2
15	≥ 5	≥ 3
20	≥ 6	≥ 3
25	≥ 7	≥ 4
30	≥ 9	≥ 4
35	≥ 10	≥ 5
40	≥ 11	≥ 5

[figure not shown]
CRS = cytokine release syndrome; DLRM = dose level review meeting.

#### 4. Covariates and Subgroups

##### 4.1 Planned Covariates

The relationship of covariates to efficacy endpoints will be explored if appropriate.

##### 4.2 Subgroups

**Subgroup analysis for those treated with siltuximab will be evaluated, including CRS outcomes, safety, and PK data.**

#### 5. Definitions

##### Age at Enrollment

Subject age at enrollment will be collected using the age in years in the clinical database.

##### AUC0-last

Area under the concentration-time curve from time 0 (time of investigational product administration) to the time of the last quantifiable concentration.

##### Baseline

Except ECG for any variable, unless otherwise defined, baseline is the last assessment taken prior to the first investigational product administration.

##### ECG analysis value

The mean value of triplicate will be calculated and used in the analysis. If an ECG is missing within a triplicate, all available data will be averaged for that time point. Further, unscheduled ECG measurements taken up to 5 minutes after the last assessment of a triplicate at a time point will be included in the mean for that time point.

### Baseline ECG

Baseline ECGs will be collected  $\geq 30$  minutes apart, with each baseline ECG in triplicate (ie, triplicate must be done approximately 30 seconds apart)

- 2 sets collected at screening, and
- 1 set collected pre-dose on cycle 1 day 1 [ie, total  $\geq 9$  ECGs])

The mean of the values within a triplicate should be calculated before taking the mean of the triplicate averages. Where an ECG is missing within a triplicate, all available data will be averaged for that time point.

### Percent Change from Baseline

Percent change from Baseline is the arithmetic difference between post-Baseline and Baseline divided by Baseline values times 100.

Percent change from baseline =  $[(\text{Post-baseline Value} - \text{Baseline Value}) / \text{Baseline Value}] \times 100$

### Fold change from Baseline

Fold change from Baseline equals the post-Baseline value divide by the Baseline value.

Fold change from baseline =  $\text{Post-baseline Value} / \text{Baseline Value}$

### Cmax

Maximum observed serum concentration.

### Cmin

Minimum observed serum concentration

### End of Study (For an Individual Subject)

An individual subject is considered to have completed the study if he/she has completed SFU visit for subjects enrolled in the dose escalation phase, or LTFU visit for subjects enrolled in the dose expansion phase as shown in the Schedule of Assessments. The SFU visit should occur approximately 4 weeks (or up to 7 days thereafter) after the last dose of AMG 427 or prior to the initiation of other AML therapy, whichever occurs earlier. End of study (EOS) for an individual subject is defined as the last day that protocol specified procedures/assessments are conducted for the individual subject.

### **End of Study:**

**End of study is defined as when the last subject is assessed or receives an intervention for evaluation in the study; if the study includes multiple parts (eg, safety follow-up or survival assessment), the end of study would include these additional parts.**

### Enrollment Date

Enrollment date is defined as the date when the investigator confirms that the subject has met all eligibility criteria and will be collected on the enrollment eCRF.

#### Change from Baseline

Change from Baseline is the arithmetic difference between post-Baseline and Baseline.

Change (absolute) from Baseline= (Post-baseline Value – Baseline Value)

#### Study Day

Post study day 1: study day= (date - date of Study Day 1) + 1

Pre study day 1: study day= (date – date of Study Day 1)

#### Study Day 1

Study day 1 is defined as the first day of administration of the investigational product after enrollment. The day prior to Study Day 1 is considered Day -1.

#### Investigational Product

The term 'investigational product' is used in reference to AMG 427.

#### Treatment-Emergent Adverse Event (TEAE)

Treatment-emergent adverse events are events categorized as Adverse Events (AEs) starting on or after the first dose of investigational product (AMG 427), as determined by the flag indicating if the adverse event started prior to the first dose (AMG 427) on the Events CRF and up to and including 30 days after the end of investigational product (AMG 427) or the end of study (EOS) date, whichever is earlier.

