9.2 Safety Event Reporting Procedures

9.2.1 Adverse Events

9.2.1.1 Reporting Procedures for Adverse Events That do not Meet Serious Criteria

The investigator is responsible for ensuring that all adverse events observed by the investigator or reported by the subject that occur from the time of consent through **30 days after the last day of the dosing interval of investigational product/safety follow-up visit (whichever occurs later)**, are reported using the Events CRF. Adverse events will be collected up to the safety follow up visit.

The investigator must assign the following adverse event attributes:

- Adverse event diagnosis or syndrome(s), if known (if not known, signs or symptoms),
- Dates of onset and resolution (if resolved),
- **Assessment of seriousness,**
- Severity (and/or toxicity per protocol),
- Assessment of relatedness to investigational products or study procedure/activity, and
- Action taken.

The adverse event grading scale used will be the CTCAE, version 4.0. The grading scale used in this study is described in [Appendix A](#). Exception: CRS will be graded according to the guidelines provided in [Table 6](#) (based on the adopted grading system referenced in Lee et al, 2019) and **ICANS will be graded according to the guidelines provided in [Table 8](#) (based on the grading system referenced in the publication by Lee et al, 2019).**

The investigator must assess whether the adverse event is possibly related to the investigational product. This relationship is indicated by a “yes” or “no” response to the question: Is there a reasonable possibility that the event may have been caused by the investigational product, and/ or study procedure/activity?

The investigator is responsible for reviewing laboratory test results and determining whether an abnormal value in an individual study subject represents a clinically significant change from the subject’s baseline values. In general, abnormal laboratory

findings without clinical significance (based on the Investigator's judgment) are not to be recorded as adverse events. However, laboratory value changes that require treatment or adjustment in current therapy are considered adverse events. Where applicable, clinical sequelae (not the laboratory abnormality) are to be recorded as the adverse event.

The investigator is expected to follow reported adverse events until stabilization or reversibility.

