9.2.1.2 Reporting Procedures for Serious Adverse Events

The investigator is responsible for ensuring that all serious adverse events observed by the investigator or reported by the subject that occur after signing of the informed consent through **30 days after the last day of the dosing interval of investigational product/safety follow-up visit, whichever occurs later**, are recorded in the subject's medical record and are submitted to Amgen. All serious adverse events must be submitted to Amgen within 24 hours following the investigator's awareness of the event via the Events CRF.

If the electronic data capture (EDC) system is unavailable to the site staff to report the serious adverse event, the information is to be reported to Amgen via an electronic Serious Adverse Event (eSAE) Contingency Report form within 24 hours of the investigator's awareness of the event. See [Appendix B](#) for a sample of the serious adverse event worksheet/electronic Serious Adverse Event Contingency Report form. For EDC studies where the first notification of a serious adverse event is reported to Amgen via the eSerious Adverse Event Contingency Report Form, the data must be entered into the EDC system when the system is again available.

The investigator must assess whether the serious adverse event is possibly related to the investigational product or study procedure. This relationship is indicated by a "yes" or "no" response to the question: Is there a reasonable possibility that the event may have been caused by the investigational product and/or study procedure? Relatedness means that there are facts or reasons to support a relationship between investigational product/study procedure/activity and the event.

The investigator is expected to follow reported serious adverse events until stabilization or reversibility.

New information relating to a previously reported serious adverse event must be submitted to Amgen. All new information for serious adverse events must be sent to

Amgen within 24 hours following awareness of the new information. If specifically requested, the investigator may need to provide additional follow-up information, such as discharge summaries, medical records, or extracts from the medical records.

Information provided about the serious adverse event must be consistent with that recorded on the Event CRF.

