9.2.1.3 Reporting Serious Adverse Events After the Protocol-required Reporting Period

During the Long Term Follow-up period, if the investigator becomes aware of serious adverse events suspected to be related to investigational product after the protocol-required reporting period (as defined in Section 9.2.1.2) is complete, then these serious adverse events will be reported to Amgen within 24 hours following the investigator's awareness of the event on the Events CRF.

After End of Study, there is no requirement to actively monitor study subjects after the study has ended with regards to study subjects treated by the investigator. However, if the investigator becomes aware of serious adverse events suspected to be related to investigational product, then these serious adverse events will be reported to Amgen within 24 hours following the investigator's awareness of the event.

Serious adverse events reported outside of the protocol-required reporting period will be captured within the safety database as clinical trial cases and handled accordingly based on relationship to investigational product. If further safety related data is needed to fulfill any regulatory reporting requirements for a reportable event, then additional information may need to be collected from the subject's records after the subject ends the study.

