10. STATISTICAL CONSIDERATIONS

10.1 Study Endpoints, Analysis Sets, and Covariates

10.1.1 Study Endpoints

Primary Endpoint:

[figure not shown]
Safety:

- Dose limiting toxicities (DLTs), treatment-emergent adverse events (TEAEs), and treatment-related adverse events (TRAEs)

Secondary Endpoints:

- AMG 427 PK parameters including, but not limited to, maximum serum concentration (C_{max}), minimum serum concentration (C_{min}), area under the concentration-time curve (AUC), and if feasible, half-life ($t_{1/2}$) of AMG 427
- Efficacy parameters for R/R AML: subject response to treatment with AMG 427 (response defined as complete response/remission [CR]/ complete response/remission with incomplete recovery of peripheral blood counts [CRi], morphologic leukemia-free state, partial remission [per modified IWG criteria]), complete response/remission with partial hematologic recovery (CRh), and duration of response (duration of response will only be measured for subjects treated with the dose and schedule of the expansion cohort)
- Efficacy parameters for MRD+ AML: subject response to treatment with AMG 427 (response refers to conversion from MRD+ status to MRD- status), relapse free survival and overall survival (relapse free survival, and overall survival will only be measured for subjects in expansion cohort)

Exploratory Endpoints:

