#### Treatment-Related AE

A treatment-related AE is any treatment-emergent adverse event that per investigator review has a reasonable possibility of being caused by the investigational product.

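### The SAP counts an AE as treatment-related only if it is also treatment-emergent, so related events that start after day 30 and are collected under the protocol drop out of the TRAE part of the primary endpoint

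*SAP*

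**What the plan says.** Protocol Section 10.1.1 sets the primary safety endpoint as "Dose limiting toxicities (DLTs), treatment-emergent adverse events (TEAEs), and treatment-related adverse events (TRAEs"). The protocol gives no TEAE window of its own; the only one is in SAP Section 5. There a TEAE starts on or after the first dose and "up to and including 30 days after the end of investigational product (AMG 427") "or the end of study (EOS) date, whichever is earlier". The next definition builds on it: "A treatment-related AE is any treatment-emergent adverse event that per investigator review has a reasonable possibility" of being caused by the product.

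The collection rules are in Protocol Section 9.2.1. Non-serious AEs are collected through "30 days after the last day of the dosing interval of investigational product/safety follow-up visit (whichever occurs later"), and Section 9.2.1.2 sets the same limit for SAEs ("investigational product/safety follow-up visit, whichever occurs later"). Section 9.2.1.1 then adds that AEs are collected up to the safety follow-up (SFU) visit, which does not fit easily with a later-of-two rule. Protocol Section 9.2.1.3 extends reporting on the Events CRF into long-term follow-up (LTFU), "if the investigator becomes aware of serious adverse events suspected to be related to investigational product". LTFU applies to expansion subjects only and lasts up to 2 years from first dose (Protocol Section 7.2.5).

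The SFU visit is due about 4 weeks after the last dose, with up to 7 days' grace, or sooner if other AML therapy starts (Protocol Section 3.5.2). Escalation subjects complete the study at that visit, and Protocol Section 7.2.4 sets a 30-day minimum for safety follow-up.

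**The concern.** The two documents cut in opposite directions: the analysis window takes the earlier of two dates and the collection window takes the later. For ordinary TEAEs this matters little, since a sponsor may collect for longer than it tabulates. The difficulty is the nesting of TRAEs inside TEAEs. Attribution by the investigator is what identifies a late event as drug-related, and the protocol asks for such SAEs specifically in LTFU. Under the SAP, that judgement has no effect once onset is past the window. An SAE that the investigator attributes to AMG 427 could be on the Events CRF and yet not count as treatment-related. Any error from this goes one way, toward fewer related events.

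**Working it through.** The plan attaches no numerical figure to this definition, so the check is a comparison of windows. Days are counted from the last dose.

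**Inputs.** SFU on about days 28 to 35, or earlier before new AML therapy (Protocol 3.5.2). Collection end: later of 30 days and SFU (Protocol 9.2.1.1, 9.2.1.2). TEAE end: earlier of 30 days and EOS (SAP 5). EOS for a subject: the final day of planned procedures for that subject (SAP 5).

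**Formulas.** Collection end = max(30, SFU day). TEAE end = min(30, EOS day). Gap = collection end − TEAE end. For escalation, assume EOS = SFU day. For expansion, assume the subject enters LTFU, so EOS is after day 30. Both treat the dosing interval as ending on the day of the last dose.

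| SFU day | Collected to | TEAE end, escalation | Gap | TEAE end, expansion | Gap |
|---|---|---|---|---|---|
| 14 (assumed early visit) | 30 | 14 | 16 | 30 | 0 |
| 21 (assumed early visit) | 30 | 21 | 9 | 30 | 0 |
| 28 | 30 | 28 | 2 | 30 | 0 |
| 30 | 30 | 30 | 0 | 30 | 0 |
| 33 | 33 | 30 | 3 | 30 | 3 |
| 35 | 35 | 30 | 5 | 30 | 5 |

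The rows for days 33 and 35 do not depend on how EOS is read. The escalation gaps for visits before day 30 do, because they need AE collection to continue to day 30 while EOS is fixed at the visit.

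**LTFU, expansion only.** Taking 2 years as 730 days, the span in which a related SAE is reportable but cannot be a TRAE is 730 − (study day of last dose + 30). For an assumed last dose on study day 8: 730 − 38 = 692 days. For study day 365: 730 − 395 = 335 days.

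**Sensitivity to "dosing interval".** The term is not defined. If it runs to the end of the cycle, collection extends to (14 − 8) + 30 = 36 days after a last dose on D8 of a 14-day cycle, or (28 − 19) + 30 = 39 days after a last dose on D19 of a 28-day cycle. The mismatch with 30 days is then 6 or 9 days.

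**What would close the gap.** Moving the TEAE end to the collection end would bring the table's gaps to zero but would leave the LTFU events out. Only separating TRAEs from the TEAE window brings those in.

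**The case against.** The case for leaving the text alone has substance. A 30-day TEAE window is not an error and matches the protocol's own minimum safety follow-up. It runs from first dose through every cycle and infusion-free interval. It works on onset, so a cytopenia that starts inside it counts however long it lasts. At the anticipated half-life of about 5 days, 30 days is 30/5 = 6 half-lives. The DLRT reviews data from after the DLT window, and a late related event can still be made a DLT, within the same primary endpoint. LTFU reporting is passive, may rest on telephone contact and exists only in expansion, so pooling late events with the rest would mix two kinds of ascertainment.

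A reader might also infer more than the documents support:

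- That SAP Section 10 is wrong to declare no changes. It is not shown to be: the protocol defines no TEAE window for the SAP to depart from.
- That an SFU visit on day 28 always loses 2 collected days. If collection to day 30 counts as a planned procedure, EOS is not before day 30. If collection stops at the visit, nothing later is collected. The loss needs a mixture of the two readings.
- That collection runs to 36 days. That rests on one reading of an undefined term.
- That late related deaths are missing from the fatal-event tables. SAP Section 9.6.2 does not say whether its SAE and fatal summaries are limited to TEAEs. Protocol Section 10.5.2 words those tables as treatment-emergent and treatment-related, so the position is unclear.

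These points narrow the finding. They do not answer the nesting: the DLT route needs a unanimous DLRT decision, and neither that route nor an unrestricted SAE table makes the event a TRAE.

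**Conclusion.** The point holds for TRAEs. Followed as written, the SAP excludes from the treatment-related results any event judged related that starts more than 30 days after the end of AMG 427, even though the protocol has it recorded. That covers AEs on days 31 to 35 when the SFU visit falls there, in either phase, and suspected related SAEs in LTFU among the approximately 90 planned expansion subjects. A shortened window in escalation is possible but conditional on EOS being taken as an SFU visit before day 30; if so, the window falls below the protocol's 30-day minimum. The documents do not allow an estimate of how many events are affected, so this is not evidence that the primary endpoint is materially biased. It is a definition that discards investigator attribution for late events, and it should be corrected before the primary analysis.

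**What to change.** In SAP Section 5:

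1. Keep the 30-day TEAE window.
2. Define a treatment-related AE as any AE with onset on or after the first dose of AMG 427 that the investigator judges related, whether or not it falls in the TEAE window.
3. Show related events with onset after the window, including all late related SAEs and deaths, as a separate line or listing by phase (escalation, expansion), with a flag for onset after new anti-AML therapy.
4. Remove the EOS limit from the TEAE definition, or state that it cannot shorten the window below 30 days for events already collected.

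In SAP Section 9.6.2, state whether the SAE and fatal tables are limited to TEAEs. The two statements on the end of AE collection in Protocol Section 9.2.1.1 should be reconciled.

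The cost is SAP wording, one listing and slightly higher TRAE counts; no new data are needed. The late events in expansion rest on passive reporting and have no equivalent active follow-up in escalation, which is why they belong on a separate line.
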